8.1.5. AUR or BPH-Related Surgical Intervention

All AUR and BPH-related surgery events during participation in the study are recorded. Subjects who discontinue from the study are followed for AUR and BPH-related surgery until the 24 month anniversary of randomization. This follow-up is in terms of biannual telephone contacts beginning at the first six month scheduled interval after discontinuation. Analyses will be in terms of events recorded at clinic visits and also collected in the biannual telephone contacts. [Table 4](#) provides an overview of the planned summaries and analyses. A list of planned data displays is in [Appendix 15](#): List of Data Displays.

Time to first AUR or BPH-related surgery will be defined as the number of days from treatment start date to date of the first event (earliest occurring of either AUR or BPH-related surgery) for each subject. Time to first AUR or BPH-related surgery is classified as a secondary efficacy endpoint and will be analyzed in terms of the Intent-to-Treat population.

Censoring will occur at the earliest of the following dates as applicable: the date of prostatectomy, the date of last contact for AUR and surgical intervention, and the date of death. For censoring, 'prostatectomy' will be determined from the eCRF prostatic surgical intervention log using the following codes associated with 'prostatectomy': open, retropubic with or without nerve-sparing, suprapubic, transvesical, perineal, salvage, laparoscopic, laparoscopic assisted. Note this excludes 'partial prostatectomy'.

The 'date of last contact for AUR and surgical intervention assessment' will be assigned as the latest of:

- Date of last treatment-phase visit
- and
- Date of last successful biannual follow-up telephone contact.

Partial dates will be handled as described in Appendix 7, Premature Withdrawals & Handling of Missing Data.

The number of subjects having the first AUR or BPH-related surgery event on or after treatment start will be tabulated by treatment, by the two annual time periods (Month 12 and Month 24), as well as by three month intervals (quarterly) along with the number of subjects at risk during each of these time periods.

Note: Cut-off dates are defined in [Appendix 6](#); definition is repeated here:

Month k Cut-off Date (for k= 3, 6, 9, 12, 15, 18, 21, 24): The maximum of [Month k clinic visit date, Month k lab visit date, Baseline Date + (k * 91/3)].

The primary analysis of this endpoint will compare combination treatment versus tamsulosin treatment in terms of time to first AUR or BPH-related surgery for the ITT population using a log rank test stratified by cluster at the 0.05 level of significance. The relative risk (hazard ratio) for the treatment effect and associated two-sided 95% confidence intervals will be estimated using a Cox proportional hazards model with treatment as the only covariate and stratified by cluster. Estimates and corresponding confidence intervals for the relative risk (hazard ratio) and risk reduction (1-hazard ratio) of combination treatment versus tamsulosin treatment will be presented along with the log rank p-value. Assessment of the Cox modeling procedure will include examination of diagnostic plots to assess the assumption of proportional hazards and the review of results obtained by fitting separate models by cluster to assess the homogeneity of treatment effect across clusters.

Time to first AUR or BPH-related surgery, expressed as months, will be summarized by treatment group for the ITT population using product-limit estimates computed by the Kaplan-Meier method and displayed graphically as Kaplan-Meier curves.

The number of subjects with at least one AUR or BPH-related surgery will be summarized by treatment group across the 2 year period. The crude rate of AUR or BPH-related surgery incidence will be calculated using the Intent-to-Treat population of each treatment as the denominator; the associated 95% confidence interval will be output. This crude rate will be compared for combination treatment versus tamsulosin treatment using the Mantel-Haenszel test stratified by cluster at the 0.05 level of significance.

AUR or BPH-related surgery event details per subject will be summarized by treatment and will include: event component (first occurring of either AUR or BPH-related surgery) and time period of first occurring event (during treatment or after treatment stop). BPH-relatedness (yes/no) and AUR precipitating factors will be summarized by treatment for subjects in which AUR is the primary efficacy event's initial component. Types of surgery/intervention will be summarized by treatment for subjects in which BPH-related surgery is the primary efficacy event's initial component.

Time from last dose to first AUR or BPH-related surgery event will be summarized for those subjects experiencing the first event after treatment stop.

Hospitalization details for the initial AUR will be summarized by treatment group for patient admission status (inpatient or outpatient). For inpatients, the ward type and hospitalization days will be summarized by treatment.

The frequency and percentage of subjects with multiple AUR or BPH-related surgery events will be summarized by treatment. The frequencies of subjects with 2 events, 3 events, or ≥ 4 events will be summarized. Among subjects with both events, the pattern of occurrence (AUR/Surgery or Surgery/AUR) will be summarized.

The above described summaries and analyses of AUR or BPH-related surgery will be repeated, when applicable, for the individual components 1) AUR and 2) BPH-related surgery.

All AUR and surgical intervention data will be listed by treatment and subject. Time to first AUR or BPH-related event will be listed for each subject along with the dates used in the computation of these values.

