4. ANALYSIS POPULATIONS

Analysis populations are defined in the following table.

Population	Definition / Criteria	Analyses Evaluated
Intent-To-Treat (ITT)	
 Comprised of all randomized subjects regardless of whether or not treatment was administered This population will be based on the treatment to which the subject was randomized. Any subject who receives a treatment randomization number will be considered to have been randomized. 	
 All.
Per-Protocol (PP)	
 Comprised of all ITT subjects who comply closely with the protocol. Specifically this includes ITT subjects who do not have a deviation which requires exclusion from the PP population. Protocol deviations that would exclude subjects from the PP population are defined in Section 4.1.3 (Deviations which Require Exclusion from the Per-Protocol Population) and Appendix 1 (Exclusions from the Per-Protocol Population). The PP population will not be analyzed if this population comprises more than 80% of the ITT population. 	
 Primary efficacy endpoint only if this population comprises 80% or less of the ITT Population. Details on specific summaries and analyses are outlined in Section 7, Primary Statistical Analyses.

NOTES :

- 'All Enrolled Subjects' is referenced in at least one tabular summary. Enrolled subjects include those who entered placebo run-in phase and/or who were randomized.

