8.2. Safety Analyses

Safety summaries and analyses are reported in terms of the following data classifications: adverse events, clinical laboratory assessments (haematology and clinical chemistry), total serum prostate specific antigen (PSA), qualitative breast examination, digital rectal examination, vital signs, suicidality, and post void residual volume.

All safety analyses will be performed using the ITT population unless otherwise specified in text or data display shells. Applicable safety analysis and reporting definitions and presentations within “Program Safety Analysis Plan (PSAP, 2016) for GI198745 (dutasteride) and GSK2285985 (fixed dose combination of dutasteride [GI198745] and tamsulosin [GI138525])” are utilized within this RAP, with any deviations noted.

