
From the above standards and principles as well as to be aligned with historical reporting for this compound and indication, the key reporting standards to be applied are:
 
 All data will be reported according to the actual treatment the subject received unless otherwise stated. Within listings, numeric data will be reported at the precision collected on the eCRF. The reported precision from non eCRF sources will follow the IDSL statistical principles but may be adjusted to a clinically interpretable number of decimal places. Within tabular summaries, the minimum and maximum values are presented with the same 	

Reporting Standards

number of decimal places as the raw data collected on the eCRF. The mean and percentiles (e.g. median, Q1, and Q3) are presented using one additional decimal place. The standard deviation and standard error are presented using two additional decimal places.

- Continuous variables (e.g., age) will be summarized using the number of observations (n), mean, standard deviation (SD), median, minimum, and maximum.
- Categorical variables will be summarized using the number of subjects (n) and percentage (%) in each category.
- P-values greater than 0.10 will be reported to two decimal accuracy. P-values less than or equal to 0.10 will be reported to three decimal accuracy. P-values less than 0.001 will be reported as '<0.001'.
- Applicable safety analysis and reporting definitions and presentations within "Program Safety Analysis Plan ([PSAP](#)) for GI198745 (dutasteride) and GSK2285985 (fixed dose combination of dutasteride [GI198745] and tamsulosin [GI138525])" will be referenced; any deviations will be noted within this RAP.

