11.6. Appendix 6: Derived and Transformed Data

(Placebo) Run-In Start and Stop Dates

- Placebo run-in start date = Start date of (placebo) study treatment recorded for the run-in period. If the recorded start dates for the two study drug containers differ, then select the earlier start date.
- Placebo run-in stop date = End date of (placebo) study treatment recorded for the run-in period. If the recorded stop dates for the two study drug containers differ, then select the later stop date.

Note: a subject with a nonmissing placebo run-in start date will be considered as included in the Placebo Run-in Phase.

Randomization Date

- Randomization date is the randomization telephone call in date which is recorded in the eCRF. This date is defined here for completeness and no derivations are made.

Note: a subject with a nonmissing randomization number recorded in eCRF will be considered Randomized.

(Double-Blind) Treatment Start and Stop Dates

- Treatment start date = Start date of study treatment recorded for the (double-blind) treatment period. If the recorded start dates for the two study drug containers differ, then select the earlier start date.
- Treatment stop date = Stop date of study treatment recorded for the (double-blind) treatment period. If the recorded stop dates for the two study drug containers differ, then select the later stop date.

Study Drug Exposure and Compliance

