11.8. Appendix 8: Adverse Event Time Periods and Special Adverse Event Definitions

Date-related derivations and transformations related to adverse events (AEs) are described below.

AE Onset Time since First Dose

= AE Onset Date – Treatment Start Date if treatment start date > AE onset date
= AE Onset Date – Treatment Start Date +1 if treatment start date <= AE start date
= missing otherwise

AE Duration (in days) = AE Resolution Date – AE Onset Date + 1

The timing of AEs will be categorized as follows:

- An AE is “Pre-Treatment” if the AE onset date is before the treatment start date.
- An AE is “On Treatment” if the AE onset date is on or after the treatment start date (but on or before the treatment stop date, if that is non-missing), or if the onset date is missing.
- An AE is “Post-Treatment” if the treatment stop date is non-missing, and the AE onset date is after the treatment stop date.
- An AE is “Post-Randomization” if the AE is either On Treatment or Post-Treatment.

Note: Cut-off dates are defined in [Appendix 6](#); definition is repeated here, in terms of 6-month treatment periods, since this is used to determine AE onset period:

Month k Cut-off Date (for k= 6, 12, 18, 24): The maximum of [Month k clinic visit date, Month k lab visit date, Baseline Date + (k * 91/3)].

An on-treatment AE is uniquely identified as having onset within one of the following four time periods: Months 1-6, Months 7-12, Months 13-18, or Months 19-24.

- An AE is considered to have onset in the Months 1-6 time period if it is an on-treatment AE and the onset date is on or before the Month 6 cut-off date.
- An AE is considered to have onset in the Months 7-12 time period if it is an on-treatment AE and the onset date is after the Month 6 cut-off date and is on or before the Month 12 cut-off date.
- An AE is considered to have onset in the Months 13-18 time period if it is an on-treatment AE and the onset date is after the Month 12 cut-off date and is on or before the Month 18 cut-off date.
- An AE is considered to have onset in the Months 19-24 time period if it is an on-treatment AE and the onset date is after the Month 18 cut-off date.

If the AE onset date is partially missing, the timing is determined as follows:

1. If the non-missing parts of the date (either just year or year/month) are unambiguously before the start of treatment, the AE is considered Pre-Treatment.

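### Time to AUR or BPH-related surgery is declared ITT but timed from treatment start, so randomized men with no recorded start date have no computable time

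*SAP*

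**What the plan says.** Section 4 of the SAP defines the ITT population as "Comprised of all randomized subjects regardless of whether or not treatment was administered", grouped by randomized treatment. Section 8.1.5 says that time to first AUR or BPH-related surgery is "classified as a secondary efficacy endpoint and will be analyzed in terms of the Intent-to-Treat population". The log-rank test and the Kaplan-Meier estimates are both stated to be on ITT.

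The same section fixes the time origin: the time "will be defined as the number of days from treatment start date to date of the first event". Appendix 6 (11.6) gives the definition: "Treatment start date = Start date of study treatment recorded for the (double-blind) treatment period". It provides no substitute when no such date exists.

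Men who discontinue the study are followed for these events by telephone "until the 24 month anniversary of randomization". The crude rate, compared by Mantel-Haenszel test, uses the whole ITT population of each arm as its denominator.

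For safety, section 8.2 says: "All safety analyses will be performed using the ITT population unless otherwise specified in text or data display shells". Appendix 8 (11.8) calls an adverse event post-randomization "if the AE is either On Treatment or Post-Treatment", and both of those categories depend on treatment dates.

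**The concern.** An ITT analysis should not depend on anything that happens after randomization. Having a recorded first dose is such a condition, and here it decides who has a survival time. A man without that date has no origin, although his event status may still be collected through the telephone contacts.

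Two tests of the same endpoint, each at the 0.05 level, can then rest on different sets of men. Unless the rule is settled in the text, the programmer must choose whether to drop these men or give them another origin, and that choice could be made after unblinding.

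**Working it through.** The SAP states no sample size, event count, power or number of undosed men for this endpoint, so there is no figure to reproduce. The check compares definitions.

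**Does every ITT man have a time?**

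1. Membership: all randomized men, dosed or not (section 4).
2. Origin: the recorded start of double-blind treatment (8.1.5, Appendix 6), with no fallback.
3. Does the SAP expect ITT men without that date? Yes. Section 6.2 counts randomized men who lack a double-blind start date. It counts men who took no dose on a separate line.
4. Does another rule supply an origin? No. The partial-date rule in Appendix 7 (11.7.2.1) moves uncertain event dates to the treatment start date, which is the missing date.
5. Result: for these men, event or censoring date minus origin is undefined. They drop out of the log-rank, Cox and Kaplan-Meier analyses but stay in the crude-rate denominator.

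**Are all post-randomization events counted?** An event after randomization but before first dose falls before the origin. It also falls outside the 8.1.5 tabulation of first events by period, which is limited to events from treatment start onward.

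**Is there a date that would serve?** The randomization date is recorded in the eCRF (Appendix 6). The SAP also defines a Baseline Date, the later of treatment start and randomization, using whichever is not missing. Section 8.1.5 uses it for the quarterly and annual cut-offs but not for the event time. It would give every ITT man an origin. For a man dosed after randomization, however, it equals the treatment start date, so an event before first dose would still precede the origin.

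**Illustrative size.** Let f be the assumed share of randomized men with no start date.

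- Expected events lost, at equal event rates, = D × f. With D assumed at 10 to 20 and f at 1% to 3%: 10 × 0.01 = 0.1 up to 20 × 0.03 = 0.6 events.
- Log-rank power by the Schoenfeld approximation, 1:1 allocation, two-sided 0.05: Φ(√(D(1 − f)) × |ln HR| / 2 − 1.96). With assumed D = 60 and HR = 0.5:

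| f | power |
|---|---|
| 0 | 76.6% |
| 0.5% | 76.4% |
| 1% | 76.1% |
| 2% | 75.7% |
| 5% | 74.4% |

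**Safety percentages.** Displayed rate = rate among men with a start date × (1 − f), if the others contribute no classifiable event. A 10% rate displays as 9.95% at f = 0.5% and 9.5% at f = 5%. Reaching the 5% cut-off for the most common adverse events needs 5 / (1 − f): 5.03% to 5.26% over the same range.

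**The case against.** The strongest reply is that this is a narrow drafting gap with little effect. Visit 2 is both randomization and the start of the treatment phase, and double-blind drug is first dispensed there, so the scheduled gap is minimal. The SAP nowhere says that these men are excluded; that is inferred from a missing date and the absence of a rule. Both statements are right. They limit the size of the problem but do not supply the missing origin.

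A reader might infer more than the text supports:

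- **That every never-dosed man drops out.** Section 6.2 separates men who took no dose from men with no start date. Per-protocol deviation 03 (Appendix 1) identifies non-consumers by a non-missing compliance of zero. Compliance needs non-missing exposure, hence a recorded start date. Such a man has a time and stays in the log-rank.
- **That the telephone follow-up contradicts the origin.** Its randomization-based limit sets how long discontinued men are followed, not where time starts.
- **That a never-dosed man cannot contribute a post-randomization adverse event.** Appendix 8 treats an event with a missing onset date as on-treatment, and likewise a partial date that cannot be placed before or after treatment. Only fully dated events in men with no start date cannot be classified.
- **That the SAP contradicts itself on the arm for a mis-dosed man.** Section 11.5.2 says "All data will be reported according to the actual treatment the subject received unless otherwise stated". Section 4 does state otherwise for ITT, and section 8.2 puts safety on ITT, so the text largely resolves to the randomized arm. What remains is that his adverse events are then reported under a treatment he did not receive.

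Using ITT for safety is also a declared choice. Exceptions may stand in the display shells, which are separate documents not at hand. That is why the safety part is secondary.

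**Conclusion.** The point holds for the efficacy endpoint. Section 8.1.5 promises an all-randomized analysis and fixes an origin that some randomized men are expected to lack, so the log-rank and the crude-rate test can use different sets. Events between randomization and first dose are also lost to the time-to-event analysis. This should be corrected, because the stated rule does not give the declared analysis.

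The numerical effect is probably small. Every value of f, the event counts and the hazard ratio above are assumptions; only the definitions come from the SAP. Within the assumed ranges, less than one event is expected to be lost among 10 to 20, and power falls by about two percentage points at most for 60 events and a hazard ratio of 0.5.

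The safety part is optional. ITT denominators slightly dilute adverse event percentages when men with no start date are included, and a mis-dosed man's events sit in his randomized arm. The fault does not extend to all safety displays: the exposure-based Tables 3.13 and 3.14 already exclude men with missing exposure, and the laboratory and vital-sign summaries of threshold values at baseline already require a post-baseline value.

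**What to change.** In section 8.1.5, measure time to first AUR or BPH-related surgery from the randomization date for all ITT men, and do the same for the two components. Use the same date as the lower limit in the tabulation of first events by period, and in place of treatment start in the Appendix 7 (11.7.2.1) partial-date rules for this endpoint. Substituting the existing Baseline Date is a smaller edit, but it repairs only the missing times and not the events before first dose.

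Optionally, define in section 4 a dosed-only safety set, analysed by treatment received, and use it for the adverse event percentage tables.

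The efficacy change costs only SAP wording, since the date is already collected. The optional change needs one population flag. Its downside is that safety denominators may differ by a few men from earlier ITT-based tables.

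### The two-year AUR/surgery proportion is a crude ITT rate that counts men with incomplete follow-up as event-free; a Month 24 estimate that accounts for censoring would be a cheap improvement

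*SAP*

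**What the plan says.** SAP Section 2.2 lists time to event and proportion of subjects together as one secondary endpoint, for the composite of AUR or BPH-related surgery and for each component. Section 8.1.5 then sets out two analyses.

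- **Time to first event.** This is named the primary analysis of the endpoint. Arms are compared "using a log rank test stratified by cluster at the 0.05 level of significance", with a Cox hazard ratio, and the data are summarised "using product-limit estimates computed by the Kaplan-Meier method and displayed graphically as Kaplan-Meier curves". Censoring is at the earliest of "the date of prostatectomy, the date of last contact for AUR and surgical intervention, and the date of death".
- **Proportion.** "The number of subjects with at least one AUR or BPH-related surgery will be summarized by treatment group across the 2 year period". For the rate, "The crude rate of AUR or BPH-related surgery incidence will be calculated using the Intent-to-Treat population of each treatment as the denominator", with a 95% CI. "This crude rate will be compared for combination treatment versus tamsulosin treatment using the Mantel-Haenszel test stratified by cluster", at the 0.05 level.

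On follow-up, the section says: "Subjects who discontinue from the study are followed for AUR and BPH-related surgery until the 24 month anniversary of randomization". This is done by twice-yearly telephone calls, and events learned that way are included. The last-contact date rests on the last call that succeeded, so the plan expects that some calls will fail. The analyses are repeated, where applicable, for AUR and for surgery separately. Section 4 defines ITT as everyone randomized. The missing-data rules in Appendix 7 cover visit-based measures and partial event or censoring dates, but not this proportion.

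**The concern.** The two analyses treat the same man differently. If he is last contacted at Month 6 without an event, the log rank and Kaplan-Meier analyses use six months of information and then censor him. The crude rate treats him as known to be event-free at Month 24. The two-year proportion and its interval are then biased downward. If loss differs between arms, the difference in crude rates leans towards the arm with more loss even when the true risks are equal. The primary log rank does not correct the reported proportion, which Section 2.2 makes part of the endpoint and which a reader is likely to take as the two-year risk.

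**Working it through.** The plan states no sample size, event rate or loss rate for this endpoint, so there is no planned figure to reproduce. Everything below is illustration under assumed values.

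**Size of the downward bias.** Let F be the true 24-month risk and L the share lost by 24 months in the absence of an event, with both times exponential. Taking 24 months as one unit of time, λ = −ln(1−F) and μ = −ln(1−L). Then

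crude rate = λ/(λ+μ) × [1 − exp(−(λ+μ))] = λ/(λ+μ) × [1 − (1−F)(1−L)].

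Example with F = 10% and L = 10%: λ = μ, so crude = 0.5 × (1 − 0.90 × 0.90) = 0.5 × 0.19 = 9.5%, a ratio of 0.95.

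Example with F = 5% and L = 20%: λ = 0.0513 and μ = 0.2231, so crude = 0.1869 × (1 − 0.95 × 0.80) = 0.1869 × 0.24 = 4.49%, a ratio of 0.897.

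| L | Crude, F = 2% | Crude, F = 5% | Crude, F = 10% | Crude/true |
|---|---|---|---|---|
| 5% | 1.95% | 4.88% | 9.75% | 0.975 |
| 10% | 1.90% | 4.75% | 9.50% | about 0.95 |
| 20% | 1.79% | 4.49% | 8.98% | about 0.90 |
| 30% | 1.68% | 4.21% | 8.44% | about 0.84 |

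The relative bias hardly depends on F. It is zero when follow-up is complete.

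**Effect on the comparison when loss differs and the true risks are equal.** With crude rates c1 and c2, d = c1 − c2, n per arm, p̄ = (c1+c2)/2, se0 = √[2p̄(1−p̄)/n] and se1 = √{[c1(1−c1)+c2(1−c2)]/n}:

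rejection rate = Φ[(d − 1.96·se0)/se1] + Φ[(−d − 1.96·se0)/se1].

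Example with F = 10%, loss 10% against 30%, n = 300: d = 9.50% − 8.44% = 1.06 points, se0 ≈ se1 ≈ 0.0233, and the rate is Φ(−1.50) + Φ(−2.42) ≈ 7.4%.

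| F | Loss by arm | n = 200 | n = 300 | n = 500 |
|---|---|---|---|---|
| 5% | 10% / 20% | 5.18% | 5.27% | 5.45% |
| 10% | 10% / 20% | 5.37% | 5.55% | 5.93% |
| 5% | 10% / 30% | 5.77% | 6.16% | 6.94% |
| 10% | 10% / 30% | 6.59% | 7.40% | 9.04% |

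A second loss pattern points the same way. Let loss be uniform over 24 months and F = 5%. The mean of F(t) is 1 − 0.05/0.0513 = 0.0252, and crude = (1−L) × 0.05 + L × 0.0252. Loss of 15% gives 4.63%, 20% gives 4.50% and 25% gives 4.38%. Comparing 25% with 15% loss gives a ratio of 0.95 and a gap of 0.25 points, and the nominal 0.05 test rejects in about 5.2% (200 or 300 per arm) to 5.4% (500 per arm).

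**Two tests of one endpoint.** If independent, two tests at 0.05 would give 1 − 0.95² = 9.75%. They share the same events, so they are not independent. In 4,000 simulated null trials (unstratified, 300 per arm, 20% loss in each arm), the chance that either rejects was 5.85% at F = 5% and 5.73% at F = 10%. Each test alone rejected in 5.3% to 5.6%. The Monte Carlo standard error is about √(0.05 × 0.95/4000) = 0.34 points.

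**The case against.** The case for leaving the text alone is strong in several respects. The log rank is designated primary, so the analyses are already ranked. Kaplan-Meier estimates by arm are planned, and so are event counts by year and quarter with numbers at risk. The rate is openly called crude. Men who stop are telephoned up to Month 24, so the relevant L is loss of telephone contact as well as withdrawal, and it may be low. A crude proportion beside these results is conventional. All of this stands and limits the consequence. It does not make the crude rate the better estimate of two-year risk.

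Three stronger readings are tempting, and the document does not support them.

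- **That inference on this endpoint is compromised.** It is not: the designated primary analysis uses censoring and is untouched.
- **That the extra test roughly doubles the error rate.** The tests are nearly redundant, as the simulation shows. Appendix 11 makes secondary testing conditional on the primary endpoint and sets no order among secondaries, but that is a separate and general matter. What remains here is that the plan does not say outright that the Mantel-Haenszel result is only supportive.
- **That Kaplan-Meier is a clean correction.** Section 8.1.5 also censors at death and prostatectomy. Treating these as independent censoring means that one minus Kaplan-Meier can overstate the risk actually observed, above all for AUR alone. The crude rate, by contrast, correctly counts a man who dies without an event as a non-event.

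**Conclusion.** The point holds as a modest improvement to the reporting of a secondary endpoint; it is not an error that threatens a conclusion. The crude rate and its test ignore incomplete follow-up that the same section foresees and censors. At an assumed residual loss of 5% to 10%, the crude rate is about 2.5% to 5% too low in relative terms, and at 20% about 10%. The comparison is materially distorted only when loss differs substantially: 10% against 30% loss with a 10% true risk brings the nominal 5% test to between 6.6% and 9.0% for 200 to 500 per arm, while a ten-point gap in loss leaves it below 6% in the cases examined. Nothing in the document indicates how much loss occurred or in which arm, so neither the size nor the direction of any bias can be claimed. The figures assume exponential or uniform loss independent of event risk, and assumed arm sizes and risks.

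**What to change.** In Section 8.1.5, for the composite and each component:

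1. Report the Month 24 cumulative incidence by arm, and the difference with a 95% CI, as the proportion result. Use Kaplan-Meier with Greenwood variance for the composite. Use a competing-risk (Aalen-Johansen) estimate where death or prostatectomy precludes the event, notably for AUR alone.
2. State that the stratified log rank is the only formal test of this endpoint.
3. Keep the crude count, and the Mantel-Haenszel p-value if it is retained, as descriptive or supportive. Section 8.1.6 already treats the other efficacy measures this way: crude ITT rates with intervals and no formal comparison.
4. Show beside it, by arm, the number of men not followed to Month 24.

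The cost is a wording change, a Month 24 readout from Kaplan-Meier estimates already planned, and slightly more output for the competing-risk estimate and the follow-up counts. One limit remains: the new estimate still assumes that loss to follow-up is unrelated to event risk, and the text should say so.
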